4.1. Background Information

Ventricular Septal Defect (VSD) is one of the common congenital cardiac diseases, covering about 20% of all congenital cardiac diseases. In 2002, Amplatzer invented the Eccentric perimembrane ventricular septal defect occluder, and carried out clinical application in multiple countries of Europe, US and Asian, etc. Among them, the number of application in China is the maximum. Among the statistical early stage clinical trial cases with Complications of atrioventricular block unexpected occurred during early stage and follow up period after surgery, the ratio of cases in need of implanting artificial heart pacemaker reached 3.8%, even with the incidence about 4 years after operation. Since the peripheral VSD occluder with nickel-titanium membrane has shown the unexpected severe complication in clinical trial, in particular with the higher incidence of complete atrioventricular block, FDA in US has not yet ratified the clinical application for this model of occluder in US. Targeting at the insufficiency in the current occluder in application, Shanghai Shape Memory Alloy Co., Ltd autonomously developed the completely degradable occluder with Independent intellectual property rights, with the following characteristics:

- 1、 The raw materials of occluder are completely degradable, after complete endothelialization in the defect location after implanting, the occluder is gradually degraded without toxicity in the degraded products, capable of complete

- disintegration and absorption by human body, without adverse reaction and long term latent risks;
- 2、 It is avoided of the conduction block existed in NiTi alloy occluder; as well as the long term mechanical friction resulted in the injury to the peripheral tissues, even in aortic perforation, and valve damages;
 - 3、 It should be avoided of the fracture in the NiTi thread of occluder resulting in the injury and the puncture of the myocardial tissues, endocarditis, hydropericardium, and hemopericardium, fistula formation, and pericardial tamponade, etc;
 - 4、 Without Ni ion separation out caused by bioelectricity or body fluids, and blood corrosion, resulting in the Ni ion toxicity in patients, as well as the allergy in minority of patients to Ni ion and other issues;

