8.1.2 Statistical Analysis Method

- (1) Description analysis: The counting data were described with frequency number and composing rate; and the measurement data applied mean value, standard deviation,

maximum value, minimum value, as well as the median value, 25 and 75 percentiles.

- (2) Baseline demographic statistical analysis: On the basis of descriptive analysis, between the counting data groups, it applies continuous calibration χ^2 inspection, when the unit block theoretical frequency number over 25% is lower than 5, it applies the Fisher's Exact Test; for normal distribution, the comparison between different counting data groups, it applies grouping t Test; for abnormal distribution, it applies Wilcoxon Rank and Wilcoxon Rank Sum Inspection for comparison between groups.
- (3) Efficacy Analysis: For occlusion successful rate 6 months after implanting as the primary efficacy indices, it applies the adjustment of central effect with CMH Chi-square test as the method to compare between different groups, apart from the assessment for the successful rate between trial and control groups, it should also be assessed for the difference value between successful rate in different groups as well as 95% confidence interval. For other efficacy indices, the comparison method between groups is similar as the baseline analysis. For within group counting data comparison with normal distribution, it applies matched t Test; for within group counting data comparison with abnormal distribution, it applies Wilcoxon Sign Rank Test.
- (4) Safety Evaluation: Describe the case number of normal before treatment and abnormal after treatment and their percentage respectively according to the test group and control group. Described the adverse events with the case number of adverse events and their occurrence, and carried out continuous calibration χ^2 test or Fisher precision probability method test. At the same time, it shall be described in details of the embodiment for all adverse events, their degrees and relevance with the research products.
- (5) For primary efficacy indices, the statistical analysis shall be carried out under the significance level with 0.025 on single side (which correspond to 95% confidence interval on one side confidence limit), for other indices, all the statistical analysis

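### The only between-group safety inference is a difference test, which cannot show comparable or better safety for rare events such as pacemaker-requiring block, although avoiding conduction block is a leading rationale for the device

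*Combined protocol and SAP*

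**What the plan says.** Sections 3.1 and 7.1.1 give safety and efficacy as joint purposes. Section 4.1 describes severe complications of nickel-titanium occluders, "in particular with the higher incidence of complete atrioventricular block", and reports that "the ratio of cases in need of implanting artificial heart pacemaker reached 3.8%, even with the incidence about 4 years after operation". Among five advantages of the new device it lists: "It is avoided of the conduction block existed in NiTi alloy occluder".

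For safety, section 8.1.2(4) plans:
- counts and percentages, by arm, of findings that were normal before treatment and abnormal after;
- "Described the adverse events with the case number of adverse events and their occurrence", followed by a continuity-corrected chi-square "test or Fisher precision probability method test";
- a narrative: "it shall be described in details of the embodiment for all adverse events, their degrees and relevance with the research products".

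Section 8.1.2(5) sets two-sided 0.05 for everything except the primary endpoint. Section 8.9 runs safety on the full analysis set. The flow chart in section 7.2 schedules an ECG at screening, during and after the operation, and at 1, 3 and 6 months. Section 8.2.1 sizes the trial at 54 per arm on 6-month occlusion success alone. Section 8.1.2(3) asks for a difference and 95% confidence interval for that endpoint; 8.1.2(4) asks for neither.

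**The concern.** A test of difference can only reject equality. When few events are expected it will usually not reject, whether the new device is better, the same or moderately worse. Failure to reject is therefore not evidence of comparable safety, still less of an advantage.

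This matters more for conduction block than for an ordinary adverse event, because section 4.1 offers its avoidance as a benefit of the device and section 3.2 says the 6-month summary will support product registration. The plan names no conduction outcome and no measure of uncertainty for any adverse event. A reader of the report would have counts and a p-value, and nothing to show how large a difference the data leave open.

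**Working it through.** **Inputs.** 54 per arm, 1:1 (8.2.1); two-sided 0.05 (8.1.2(5)); Fisher or corrected chi-square (8.1.2(4)); 3.8% needing a pacemaker (4.1). The documents give no rate for the test arm, for the trial's own control device, or for conduction block of any grade. All other rates below are assumptions, shown as a range.

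**The plan's own figure.** With 98% success in both arms, margin 8%, one-sided 0.025 and 80% power, the formula in 8.2.1 gives n = (1.960 + 0.842)² × 2 × 0.98 × 0.02 / 0.08² = 48.07. Allowing 10% loss, 48.07 / 0.9 = 53.4, so 54. The figure reproduces, and it contains no safety component.

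**What Fisher's test needs.** Against zero events in 54, five control events give p = 0.057 and six give p = 0.027. Significance therefore needs at least 6 v 0. At 3.8% the expected number is 54 × 0.038 = 2.05.

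**Exact power,** summing over two independent binomials with 54 per arm. Fisher and the corrected chi-square agree in every row.

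| Control v test | Power |
|---|---|
| 3.8% v 0% | 1.6% |
| 3.8% v 1% | 1.0% |
| 3.8% v 1.9% | 0.6% |
| 3.8% v 7.6% (doubling) | 4.4% |
| 3.8% v 10% (harm) | 11.5% |
| 5% v 0% | 5.2% |
| 8% v 0% | 26% |
| 10% v 0% | 46% |
| 15% v 0% | 84% |
| 10% v 5% | 7% |
| 15% v 7.5% | 14% |
| 20% v 10% | 21% |

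With 49 per arm, 3.8% v 0% falls to 1.0%.

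**What an interval would show.** For 0/54 the exact two-sided 95% upper limit is 1 − 0.025^(1/54) = 6.6%; the one-sided limit is 1 − 0.05^(1/54) = 5.4%. Both exceed 3.8%. If the true rate were 3.8%, an arm of 54 would still show no events with probability 0.962^54 = 12%.

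**The case against.** Low power for rare adverse events is normal in a trial sized on efficacy, and section 8.5 judges success on the occlusion interval alone. That stands: the primary conclusion is untouched. Four stronger readings are tempting and are not supported.

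- **That power is below 2% for conduction block as such.** The 3.8% concerns pacemaker implantation, a narrower event. It comes from early cases with an earlier occluder, includes onset at about 4 years, and is worded loosely enough that it might be a share of the block cases. Block of any grade must be at least as frequent as the subset needing a pacemaker, and power could be much higher. In the other direction, a 6-month pacemaker rate below 3.8% would lower power further.
- **That the safety analysis is nothing but a significance test.** Section 8.1.2(4) also plans counts, percentages and a description by severity and relatedness. Block seen on an ECG can also enter as an adverse event: section 13.2 requires all such events to be recorded, section 7.1.7 asks for severity, date, duration, treatment and result, and section 13.4 names bundle branch and atrioventricular block.
- **That the plan will read non-significance as no difference.** No section says so. It is a risk the plan leaves open.
- **That conduction block is the sole or main rationale.** Section 4.1 stresses it, but lists five advantages.

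It is also fair to say that a conduction outcome needs rules on timing. Section 13.4 says block during the operation usually resolves, so a single undivided count would mix different events.

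**Conclusion.** The point holds in limited form. The only between-group safety inference in 8.1.2(4) is a difference test, and that test cannot establish comparable or better safety for rare events. For pacemaker-requiring block at an assumed 3.8% in the control arm, it would miss complete elimination about 98% of the time and a doubling about 96% of the time. For block of any grade the power is unknown. Among the assumed rates examined, it exceeds 80% only when block is common and abolished (84% at 15% v 0%), and it stays at 7% to 21% if rates of 10% to 20% are halved.

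The planned descriptive reporting remains useful, but it does not quantify uncertainty or single out conduction events. This is a cheap improvement to the safety analysis. It is not a flaw in the primary comparison.

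**What to change.** Amend 8.1.2(4), keeping the planned descriptive adverse event reporting:

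1. Add a table by arm of new atrioventricular block, new bundle branch block and pacemaker implantation, separately and combined, drawn from the scheduled ECGs and the adverse event records. Show transient intraoperative block apart from block present at follow-up.
2. Give exact (Clopper-Pearson) 95% confidence intervals per arm and a 95% interval for the difference. Use a method for the difference that behaves with zero counts, such as a score interval.
3. State that a non-significant p-value will not be interpreted as evidence of equal safety.
4. State that 0/54 at 6 months, with an upper limit of 6.6%, would not exclude the cited 3.8%, and so would not by itself support the claim that conduction block is avoided. Late block lies outside the 6-month analysis; section 7.1.5.6 mentions further follow-up to 3 years.

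Section 8.8 allows changes to the analysis plan before database lock, and this one leaves the primary analysis and the analysis sets as they are. It needs no new patients or visits. The cost is one extra table, a working definition of new block with consistent ECG reading, and a less favourable safety statement.

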8.1.3. Statistical Analysis Regulation

Relevant links involved in the statistical analysis shall all comply with the prescription in ICH E9, as well as the relevant requirements in the “Biological Statistical Guiding Principles in Clinical Trial” released by CFDA. At the same time, all the analysis procedures shall all be strictly implemented according to the Standard Operation Procedures (SOP) released by Medical Statistical Department in National Cardiovascular Diseases Center.

8.2 Sample Volume Calculation

8.2.1 Total Sample Volume

It is expected of 108 cases of patients included in the trial, randomized into the trial group or control group with the ratio of 1:1, with 54 cases in each group. The calculation of sample volume is based on the primary evaluation indices, namely the 6 months occlusion successful rate after implanting.

In combination of the current clinical evidence and experience assessment by the clinical experts, it is assumed that the 6 months occlusion successful rate is about 98% after implanting in patients of the control group, it is expected the trial products in the trial group in application can also reach the same successful rate level, it is determined by clinician and sponsor after joint discussion that the non-inferiority limit value is set as 8%, when the significance level for statistical test takes 2.5% on single side, with test power of 80%, taking into account of the maximum incidence of 10% falling off rate and randomized block length in the research, according to statistical principles, it is calculated that, for each group, it is necessary for 54 cases of patients inclusion, total case number in both groups are 108 cases.

The corresponding sample volume calculation equation is:

$$n = \frac{\left[\mu_{1-\alpha} \sqrt{2\bar{p}(1-\bar{p})} + \mu_{1-\beta} \sqrt{p_T(1-p_T) + p_C(1-p_C)} \right]^2}{(\Delta - (p_T - p_C))^2}$$

In the equation p_T correspond to the 6 months occlusion successful rate after implanting in trial group, and p_C represents 6 months occlusion successful rate after implanting in control group; $\bar{p} = (p_T + p_C)/2$ is average successful rate between both groups; Δ corresponds to non-inferiority limit value; μ represents the percentile of standard normal distribution, α corresponds to Type I error level for statistical test, which is 0.025 here, while β corresponds to Type II error level for test, when calculated, it takes 0.2 (corresponding to 80% of test power).

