8.1. Statistical Design, Method and Analysis Regulation

8.1.1 Statistical Design (Hypothesis Inspection)

The current trial adopts perspective, multiple centered, randomized control design and the comparing type is non-inferiority trial. Through the comparison with the similar products already marketed, it has been proved that the trial instrument can meet the clinical application needs in the same way, and for the primary evaluation index, it is setup as the occlusion successful rate 6 months after implanting in evaluation during operation, and the corresponding statistical hypothesis inspection is :

$$H_0 : p_T - p_C \leq -\Delta$$

$$H_1 : p_T - p_C > -\Delta$$

In the equation p_T , it corresponds to occlusion successful rate 6 months after implanting in the trial group, and p_C represents the occlusion successful level 6 month after implanting in the control group, Δ represents non-inferiority limit value (here it is positive value).

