8.3 Significance level and Test Power for Clinical Trial

In the current trial, the significance level for the statistical test shall take 5%(on both sides)(unless specified otherwise), and the test power take 80%.

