8.5 Eligible/Ineligible Criteria of Clinical Trial Results

From statistical angle, it is judged of the eligibility and ineligibility of the trial results, correspond to the validation for initial hypothesis inspection. For the current research, the primary evaluation index is the 6 months occlusion successful rate after implanting, and the comparison type of the trial is non-inferiority inspection, which is planned to be proved through trial result. Compare the trial group and control group product, they both have the same treatment efficacy.

In conclusion, the judgment of trial results shall be based on the difference between the occlusion successful rates in the trial group and the control group, if the results demonstrate: The occlusion successful rate in trial group subtracting that in control group in the lower limit of 95% confidence interval is greater than -8% (the non-inferiority limit value setup in advance), it can be explained as non-inferiority conclusion is established. Otherwise, the non-inferiority conclusion can not be reached.

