8.9 Selection Standard and Causes for subjects included into the analysis

Statistical analysis shall be based on the foundation of the following analysis population, before the initiation of statistical analysis, it would make clear definition for the analysis population, which include:

Full Analysis Set (FAS): The subject set defined according to the Intention To Treat Principle, referred to the data set of all the subjects participated in randomization and applying research devices. For patients fail to observe of the primary efficacy indices, it is planned to apply WCCF (Worst Case Carry Forward) strategy to carry out cutting and transfer for the missing data.

Per-protocol population set (PPS): Refer to all the treatment population subgroup finished the trial and excluded the severe breach of protocol (refer to research subject breaching the inclusion criteria or in compliance with the exclusion criteria, etc).

The primary efficacy indices analysis shall be carried out on the basis of Full Analysis Set and Per-protocol population set at the same time; in addition, all the baseline demographic data and secondary efficacy analysis shall be carried out on the basis of Full Analysis Set, and the safety evaluation shall also be carried out on the basis of Full Analysis Set (Therefore, it would not define SS separately).

8.10 During validation of hypothesis, it is excluded of specific information and their causes (if applicable)

Not applicable.

9. Data Management

It applies Electronic Data Capture(EDC) to complete the collection of trial data.EDC system has undergone strict testing, completely meet the requirements of “Quality Management Norm for Clinical Trial of Medical Devices”, “Data Management Work Technique Guideline for Clinical Trial”.Before the online of the system, it is necessary to carry out training and testing for the relevant application staff, to ensure that the system meet the requirement of the trial.After formal online, relevant staff would obtain the account and password.The account binds the roles and authority of the clients, and they should properly preserve the account information, and forbidden to divulge the account information to any others, or replace others in their performance of others rights.

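### Section 8.2.1 claims 80% power at one-sided 2.5% with 54 per group, but no test that holds 2.5% exceeds about 62% power at that size, and score or Newcombe limits give 46-47%

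*Combined protocol and SAP*

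**What the plan says.** Section 8.1.1 sets a null of pT − pC ≤ −Δ, "and the comparing type is non-inferiority trial". Section 8.2.1 assumes about 98% six-month success in the control group and the same in the trial group, a margin of 8 points, 1:1 allocation and at most 10% falling off. It plans for the case "when the significance level for statistical test takes 2.5% on single side, with test power of 80" per cent, and arrives at 54 per group. In its formula the α term uses the variance at p̄, which "is average successful rate between both groups". Section 8.3 repeats the power claim: "and the test power take 80" per cent.

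On the analysis side, 8.1.2(5) says that for the primary endpoint "the statistical analysis shall be carried out under the significance level with 0.025 on single side". Section 8.1.2(3) plans a centre-adjusted CMH comparison and adds that "it should also be assessed for the difference value between successful rate in different groups as well as 95% confidence interval". Section 8.5 declares non-inferiority if the "lower limit of 95% confidence interval is greater than -8" per cent. None of these sections names the type of interval. Section 8.9 states: "The primary efficacy indices analysis shall be carried out on the basis of Full Analysis Set and Per-protocol population set at the same time". In the full analysis set, missing primary outcomes take the worst case.

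**The concern.** With 98% success and 54 patients, about one failure per group is expected (54 × 0.02 = 1.08). A normal approximation to a difference of proportions is unreliable there. The formula also evaluates its α term at 98% in both groups, although the null it must protect against is a deficit of 8 points or more, where the variance is much larger.

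The 80% is the only power figure the trial gives. A reader takes from it that an equally good device has a four-in-five chance of success at a 2.5% risk of a false pass. If that pair is unattainable, then either the false-positive risk is above 2.5% or the chance of success is well below 80%. Because no interval is named, the plan does not say which.

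**Working it through.** **Inputs.** From 8.2.1: pT = pC = 0.98, Δ = 0.08, α = 0.025 one-sided, β = 0.2, 10% loss, 54 per group. From 8.5: pass if the lower 95% limit exceeds −8%. I use 54 per group (full set, no missing outcomes) and 48-49 (54 × 0.9 = 48.6 evaluable).

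**1. The plan's own figure.** With equal rates, 2p̄(1−p̄) = pT(1−pT) + pC(1−pC) = 2 × 0.98 × 0.02 = 0.0392. Then n = (1.95996 + 0.84162)² × 0.0392 / 0.08² = 48.07, and 48.07 / 0.9 = 53.4, so 54. It reproduces. The same approximation implies power of 79.9%, 80.7% and 84.4% at 48, 49 and 54. Because pooled and unpooled variances coincide here, the formula in effect plans for a Wald interval.

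**2. Variance at the null.** The restricted estimates under pT − pC = −0.08, when both true rates are 98%, are 0.9092 and 0.9892. Variance: 0.9092 × 0.0908 + 0.9892 × 0.0108 = 0.0933, which is 2.4 times 0.0392.

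**3. Exact power and error at 54 per group.** Largest number of trial-group failures that still passes:

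| Control failures | 0 | 1 | 2 | 3 | 4 |
|---|---|---|---|---|---|
| Wald | 1 | 1 | 2 | 2 | 3 |
| Newcombe / score | 0 | 0 | 1 | 2 | 2 |

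Binomial(54, 0.02) probabilities of 0 to 4 failures are 0.3359, 0.3702, 0.2002, 0.0708 and 0.0184.

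- Wald power: 0.7061 × 0.7061 + (0.2002 + 0.0708) × 0.9063 + 0.0184 × 0.9771 ≈ 0.762. Five or more control failures add about 0.004, giving 76.7%.
- Newcombe power: 0.7061 × 0.3359 + 0.2002 × 0.7061 + (0.0708 + 0.0184) × 0.9063 ≈ 0.459. The same remainder gives 46.4%.

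For error at 90% versus 98%, the trial-group failures follow Binomial(54, 0.10), with P(0) = 0.0034, P(≤1) = 0.0237, P(≤2) = 0.0834 and P(≤3) = 0.1985. The same sums give 4.4% (Wald) and 1.6% (Newcombe).

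**4. All sizes, full enumeration.** Error is one-sided.

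| Limit | Power at 98% v 98% (48 / 49 / 54) | Error at 90% v 98% | Maximum error along the margin |
|---|---|---|---|
| Wald | 79.5 / 79.0 / 76.7% | 6.3 / 5.9 / 4.4% | 9.5 / 8.8 / 6.3% |
| Agresti-Caffo | 62.3 / 61.9 / 72.5% | 3.4 / 3.2 / 3.0% | 6.3% at 54 |
| Newcombe, Miettinen-Nurminen, Farrington-Manning | 47.5 / 47.0 / 46.4% (Newcombe) | 1.6-1.7% | 2.8-2.9%, near a 54% control rate |

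For control rates of 90-100% the last row's maximum is 2.1-2.7%.

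**5. Ceiling for any method.** A linear programme over all rejection rules, randomised ones included, with error at most 2.5% along the margin, gives maximum power of 56.05% (48), 57.3% (49) and 62.45% (54). The bound at 54 can be checked with the Neyman-Pearson lemma at the single null point 91% versus 99%, which also gives 62.45%. If 2.5% is required only at 90% versus 98%, the ceilings are 58.3%, 60.1% and 71.1%.

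**6. One failure in each group of 54.**

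- Wald: −1.96 × √(2 × 0.9815 × 0.0185 / 54) = −5.1%, a pass.
- Newcombe: the Wilson limits for 53/54 are 0.9023 and 0.9967, so −√((0.9815 − 0.9023)² + (0.9967 − 0.9815)²) = −8.06%, a fail.

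**7. Size for 80% power.** Farrington-Manning: (1.95996 × √0.0933 + 0.84162 × √0.0392)² / 0.0064 = 91.5, so 92 evaluable and 92 / 0.9 = 102.2, so 103 enrolled per group. Exact power reaches 80% and stays there from 87 (Newcombe) or 88 (Miettinen-Nurminen) evaluable per group.

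**The case against.** The arithmetic in 8.2.1 is right on its own terms. For a Wald limit at 48 per group the formula predicts power well (79.9% against an exact 79.5%), so what fails there is the error rate, not the power. That is fair. It fits the conclusion, since power near 80% appears only with a limit that breaks 2.5%. At 54 even Wald gives 76.7%, against 84.4% by formula.

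Section 8.8 provides for a separate analysis prospectus, not available here, which may name the interval. It may, but the ceiling in step 5 applies to every choice.

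The planned comparison is centre-adjusted, and these calculations are not. If success rates are equal across centres, the group totals are sufficient and the ceiling binds stratified tests too.

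The protocol says about 98%. At 54 per group, Newcombe power is 41% at 97% and 61% at 99%, so 46% should not be read as precise. The ceiling is 52.9% and 75.4% at those rates, still below 80%.

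The 46% also assumes no missing outcomes, whereas the full analysis set imputes the worst case. If 10% are missing in each group and all count as failures, observed success is 0.9 × 98% = 88.2%, and Newcombe power at 54 falls to about 23% (Wald 26%). At 5% missing it is about 31% (Wald 40%). This objection stands and makes matters worse.

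Lastly, Newcombe and score limits themselves slightly exceed 2.5% far from the design rates. That is true, but it has no bearing on whether 80% is attainable.

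**Conclusion.** The concern holds. At 54 enrolled per group, the stated pair of 2.5% one-sided error and 80% power is unattainable by any method. The shortfall is at least 17 to 18 points at 54 and 23 to 24 at 48-49 against the theoretical ceiling, and about 33 points with score or Newcombe limits. Alternatively, with Wald, the true error is about 1.8 to 2.5 times the stated 2.5% at 90% versus 98%. These figures rest on the plan's own rates, margin and allocation, with equal group sizes, and before centre adjustment and worst-case imputation. If 2.5% is enforced only at 90% versus 98%, the ceiling is 71.1% at 54, still short of 80%. This should be corrected, because it is the trial's only power statement and the unnamed interval can decide the result.

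**What to change.** 1. In 8.1.2(3) and 8.5, name the interval used for the decision, for example Miettinen-Nurminen or Newcombe.
2. In 8.2.1, evaluate the α term at the non-inferiority null, or compute power exactly.
3. In 8.2.1 and 8.3, restate the power for that method and size. With score or Newcombe limits this is about 47% at 48-49 evaluable and 46% at 54, before centre adjustment and worst-case imputation. Show the range for control rates around 98% and for missing outcomes.
4. If Wald is kept, state that its one-sided error at 90% versus 98% is about 6% at 48-49 and 4.4% at 54.

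The cost is wording in four sections and a less favourable stated power. The correction itself needs no extra patients, and enrolment can stay at 108. The 80% sizes in step 7 are for information only.
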